1. STUDY OBJECTIVES

Primary Objective

This clinical trial will determine if subjects with heart failure with preserved ejection fraction (HFpEF) and type 2 diabetes mellitus (DM2) receiving sodium-glucose cotransporter 2 (SGLT2) inhibitor therapy (ertugliflozin) alters cardiac metabolism compared to placebo in a single blinded (to subject), randomized, parallel group, active controlled, single center experimental design.

Specific Aims

Aim 1: Determine if 12 weeks of SGLTi therapy improves peak exercise oxygen uptake compared to placebo. We will perform cardiac MRI exercise testing (CPETExMR) [N=52 (26 intervention / 26 control)] pre- & post 12 weeks of therapy to measure cardiopulmonary fitness by metabolic cart gas exchange and left ventricular myocardial mass. The primary endpoint of the study will be peak oxygen uptake (VO2 peak, ml/kg/min) as a measure of cardiopulmonary fitness with change in LV mass (gm/m2) as a pre-specified secondary endpoint. The impact of SGLT2i on VO2 kinetics in HFpEF remains unreported.

Aim 2: Evaluate the short term (12 weeks effect of SGLTi on metabolic flexibility in HFpEF compared to baseline function and control group. We will measure glucose and lipid metabolism response to SGLT2 inhibition. Serum samples of glucose and ketone bodies (β -hydroxybutyrate) will be assessed pre- and post-12 weeks of therapy. Fasting serum ketone bodies will be a pre-specified endpoint. Serial serum samples will allow us to generate metabolomics profiles before and after treatment. This experimental design will provide insight into ketone body production, peripheral glucose flux, and circulating lipoparticles in response to SGLTi therapy.

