3. STUDY DESIGN

The EMMED-HF trial will be a single blinded (to patient), randomized, parallel group, active controlled, single center experimental design. 52 subjects with HFpEF and DM2 will comorbidities will be recruited to participate (N = 26 ertugliflozin group, N = 26 placebo group) with a 12 week study intervention period.

Enrollment/Randomization procedure

Subjects will be screened by qualified practitioners for eligibility to participate in the EMMED-HF clinical study. Once the subject has been determined to be eligible, an enrollment visit will be scheduled. Those subjects that meet the inclusion criteria and do not possess any exclusion criteria will be deemed eligible for enrollment by key study personnel and then undergo randomization to treatment arm. Randomization into treatment group will occur at baseline at a 1:1 ratio.

Primary endpoint

The primary endpoint is to assess the degree of change in peak exercise oxygen uptake (peak VO2, ml/kg/min) as measured by metabolic gas exchange during a MRIcardiopulmonary exercise test (CPET-ExMR) protocol.

Secondary endpoints

Change in LV mass index (gm/m2) measured by MRI imaging will be a pre-specified secondary endpoint. An additional pre-specified secondary endpoint will be fasting serum β -hydroxybutyrate (ketone body).

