7.2 Statistical analysis

The results of experiments will be analyzed by several statistical methods. Continuous variables will be analysis as the group mean and standard deviation. Categorical variables will be analyzed with a χ^2 test between groups. Continuous variables will be analyzed with t test for normally distributed variables and Wilcoxon 2 sample test for skewed distribution continuous variables. ANOVA will be used for evaluation of multiple continuous variables between groups. Curve fitting functions will be used for the detection of associations, using standard software (e.g., Graph pad prism 5.0). In all cases, p<0.05 will be considered as statistical significance.

Sample Size and Power Calculations: Our power analysis is based on physiologic outcome measures of primary and secondary endpoints estimated from the reported literature on heart failure with preserved ejection fraction. Power calculations were performed in R software.

For the primary endpoint, peak exercise oxygen uptake (VO2 peak), increased VO2 peak is a marker for reduced mortality and morbidity with associated increase in cardiopulmonary fitness in heart failure with preserved ejection fraction patients.25, 26 The primary endpoint for this trial is increase in VO2 over the duration of the study period. Baseline peak VO2 exercise performance in HFpEF has been reliably reported at 11.7 ml/kg/min in the RELAX trial26 with a within-patient standard deviation for peak VO2 in HFpEF of 2.0 ml/kg/min (used for both INDIE-HFpEF and RELAX trials).25,26 To calculate the primary endpoint power, the ss.1way function with variables: (k=2, alpha=0.05, beta=.2, f=.4, B=100) was used. For a power of 80%, assuming 5% type I error and a standard deviation of 2.0 ml/kg/min, we must enroll 26 subjects to detect a 2.0 ml/kg/min change from baseline in peak VO2 difference between the mean of placebo and ertugliflozin groups based on power calculation.

A secondary endpoint of left ventricular mass by CMRI (measured concurrently to VO2 during Ex-CMR protocol) will be measured. Reduced left ventricular (LV) mass is a marker of response to heart failure therapy. A reduction of LV mass by 10 gm has been reported as a significant marker of clinical response.24 (The same group reported a standard deviation of 9.6 gm for a 10 gm mean change in LV

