mass in heart failure patients.30 For a power of 80% assuming 5% type I error, we must enroll 20 subjects to detect a 10 gm change in LV mass assuming a standard deviation of 9.6 gm.

A secondary endpoint of change in fasting serum β -hydroxybutyrate (μ mol/L) will be measured. Ferrannini et al. report fasting BHB levels of 246 (standard deviation 288) prior to exposure to empagliflozin21 with an increase to 561 after 4-week exposure to drug. For a power of 80%, assuming 5% type I error, we must enroll 18 subjects to detect a 125% increase in fasting serum β hydroxybutyrate.

	Parameter	Reference	δ (Change)	SD (ơ)	N (90% power)
Primary Endpoint:					
Oxygen uptake	VO ₂ (ml/kg//min)	25, 26	2.0	2.0	21
Secondary Endpoints					
Ventricular Mass (measured by CMRI)	MRI measured LV Mass (gm)	24	5	4	14

21

125

117

18

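### Aim 2 names the subject's own baseline as a second comparator, and 7.2 does not say that the between-arm contrast decides the fasting β-hydroxybutyrate result

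*Combined protocol and SAP*

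**What the plan says.** Section 1 states the overall objective against placebo: the question is whether ertugliflozin "alters cardiac metabolism compared to placebo in a single blinded (to subject), randomized, parallel group" design. Aim 1 also names only placebo. Aim 2 differs, because it names two comparators: "Evaluate the short term (12 weeks effect of SGLTi on metabolic flexibility in HFpEF compared to baseline function and control group". Its endpoint is then fixed: "Fasting serum ketone bodies will be a pre-specified endpoint".

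The form of that endpoint varies. Section 3 gives a level ("An additional pre-specified secondary endpoint will be fasting serum" BHB), with neither a change nor a contrast. The sizing text in 7.2 gives a change ("A secondary endpoint of change in fasting serum" BHB). Section 4.4 has BHB measured in both arms at baseline and after 12 weeks.

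Section 7.2 lists a chi-square test between groups, a t test for normally distributed variables, a two-sample Wilcoxon test for skewed ones, and a between-group ANOVA. It assigns none of these to BHB and does not say whether the t test is paired. It closes with: "In all cases, p<0.05 will be considered as statistical significance".

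**The concern.** A before/after test within one arm is not a treatment comparison. For fasting BHB it picks up regression to the mean, differences in diet or fasting before the two draws, season, and the effect of being in a trial. The placebo arm exists to remove these. Because Aim 2 lists baseline as a comparator and 7.2 names no deciding contrast, an analyst could run a paired t test in the ertugliflozin arm, find p<0.05, and report it under Aim 2 without departing from the written plan. The same holds for reporting that the change was significant on ertugliflozin but not on placebo. Neither statement tests a difference between the arms.

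**Working it through.** **1. Which contrast does the plan's own BHB figure imply?**

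Inputs from 7.2: baseline 246 µmol/L with SD 288, rising to 561 on another drug of the class; a 125% increase to be detected; N = 18. The text labels this 80% power and the table heading says 90%. The table row is broken but reads as change 125, SD 117, N 18. That agrees with percentages of baseline: 288/246 = 117%, and 1.25 × 246 = 307.5.

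Standardised effects: (561 − 246)/288 = 315/288 = 1.094, and 125/117 = 1.068.

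Two-sample formula, two-sided 0.05: n per arm = 2(z₀.₉₇₅ + z_power)²/d². One-sample or paired formula: n = (z₀.₉₇₅ + z_power)²/d².

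| Formula | 80% power | 90% power |
|---|---|---|
| Two-sample, d = 1.094 | 2(1.960 + 0.842)²/1.094² = 13.1, so 14 per arm | 2(1.960 + 1.282)²/1.094² = 17.6, so 18 per arm |
| Two-sample, d = 1.068 | 13.8, so 14 per arm | 18.4, so 19 per arm |
| Paired, normal or t, both values of d | 7 to 9 | 9 to 12 |

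Of these, only the two-sample formula at the table's 90% gives 18 (18 to 19 per arm). So the sizing is between-arm. With 26 per arm, a two-sample t test has about 97% power at either effect size. This takes 288 as the SD, although 7.2 gives it as the SD of the pre-exposure level and not of the change. The 80%/90% mismatch is a separate point.

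**2. What would a within-arm claim cost if it were made?**

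Assume normal change scores, 26 per arm (Section 3), a two-sided test at 0.05, no dropout, and the same true change in both arms, so that the drug does nothing. The documents give neither a placebo change nor an SD of change, so the shared change e is in SDs of change, and its range is assumed.

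The one-sample t statistic in the ertugliflozin arm has 25 degrees of freedom, critical value 2.060 and noncentrality e√26.

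| e | e√26 | P(ertugliflozin pre-post p<0.05) | P(significant on ertugliflozin, not on placebo) = p(1 − p) | Between-arm test |
|---|---|---|---|---|
| 0.25 | 1.275 | 23% | 18% | 5% |
| 0.3 | 1.530 | 31% | 21% | 5% |
| 0.4 | 2.040 | 50% | 25% | 5% |
| 0.5 | 2.550 | 69% | 21% | 5% |

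**3. How much depends on the joining word?**

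In a simulation under the same assumptions (100,000 trials per value of e), requiring both the within-arm and the between-arm test to succeed gave an error of 1.7% with no shared change, rising to 4.9% at 1.0 SD. Accepting either test gave 8% with no shared change and 98% at 0.8 SD. The plan states neither rule.

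**The case against.** The strongest reply is that Aim 2 joins its comparators with *and*. If placebo changes equally, the control-group comparison in that same sentence fails and the aim is not met. If both comparisons are required, the error never exceeds 5%. The surrounding text points the same way: the overall objective is against placebo, the tests in 7.2 other than the t test are two-sample or between-group, no paired test is named, and N = 18 fits only a two-sample calculation. The instruction in 4.4 to repeat tests under an identical protocol explains how change is measured; it does not specify a test. The 0.05 rule sets a level and chooses no contrast.

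Most of this stands. A reader might infer that Aim 2 lets a pre-post rise be declared a drug effect even when placebo rises equally. The documents do not support that, because nothing in them makes baseline alone sufficient.

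A reader might also extend the point to the primary endpoint, since 7.2 says "The primary endpoint for this trial is increase in VO2 over the duration of the study period". That is not supported either: Aim 1 is stated against placebo, and later in the same paragraph the trial is sized on the difference between the two groups' mean changes.

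What survives is narrower. The reassurance rests on a reading of *and* that the plan never turns into a decision rule, and no test is assigned to BHB.

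**Conclusion.** This is a gap in specification, confined to Aim 2 and fasting BHB, and closing it is a free improvement. The plan intends a between-arm comparison and sizes for one, but it does not exclude a within-arm p<0.05 as evidence of effect. The 23% to 69% range measures an analysis that the text leaves open but does not specify. It depends on an assumed shared change of 0.25 to 0.5 SD, normal change scores, two-sided testing and complete data. It is not the error rate of the plan as a whole.

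**What to change.** - **Aim 2:** replace the two comparators with a comparison against placebo, adjusting for baseline.
- **Section 7.2:** state that fasting BHB is analysed as the between-arm difference at 12 weeks by ANCOVA on baseline BHB, with a 95% CI, on the log scale if the data are skewed. The quoted SD of 288 exceeds the mean of 246 for a quantity that cannot be negative, so skew is likely. On the log scale the result is a ratio of geometric means, which suits a target stated as a percentage increase.
- **Section 7.2:** state that within-arm changes are descriptive only and carry no inferential claim.
- **Section 3:** word the BHB endpoint to match.

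The cost is a few sentences and at most one degree of freedom. Baseline BHB is already collected in both arms, so no new data and no larger sample are needed. The wording should be settled before the database is unblinded.

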2. BACKGROUND AND RATIONALE

Background/ Rationale/ Significance

Heart failure (HF) is an epidemic in patients with type 2 diabetes mellitus (DM2) with prevalence between 10-23%. This association extends to both HF with reduced ejection fraction and with preserved ejection fraction (HFpEF). Of critical importance, there are no current FDA indicated therapies for HFpEF patients. The etiology of HFpEF is heterogenous with phenotypes expressing both central cardiopulmonary and peripheral exrtramyocardial functional limitations. Multiple pathways of metabolic derangement in DM2 individuals have been proposed as mediators of diastolic dysfunction leading to clinical heart failure including: reactive oxygen species generation, advanced glycosylation end product deposition, enhanced collagen cross linking, and ectopic myocellular lipid accumulation. Several comorbidities contribute to the HFpEF phenotype including: hypertension, left ventricular hypertrophy, coronary artery disease, atrial arrhythmias, obstructive sleep apnea, dyslipidemia, and anemia. These metabolic derangements lead to impaired myocardial substrate utilization and mitochondrial dysfunction. Additionally, individuals with HFpEF and DM2 have peripheral organ (liver, adipose, skeletal muscle) insulin resistance that impairs total body energy homeostasis which may contribute to extracardiac manifestations of clinical heart failure.

The results of recent sodium-glucose cotransporter 2 (SGLT2) inhibitor therapy clinical trials demonstrate clinically significant reductions in cardiovascular endpoints (myocardial infarction, cardiac death, heart failure hospitalization). SGLT2 inhibition appears to exert cardiovascular protection through pleiotrophic effects involving both the myocardium and peripheral organs but the primary pathway of risk reduction of heart failure incidents has not been elucidated. SGLT2 inhibitors induce a loss of 50-100 grams of glucose through urinary excretion daily. There is a compensatory increase in ketone body production in the liver after initiation of SGLT inhibition. Ketone bodies are the most energy efficient myocardial fuel source and reduce myocardial oxidative stress when consumed as the primary energy substrate. Inducing a shift to ketone body metabolism to improves cardiac diastolic performance suggests a unifying paradigm of direct myocardial effect and peripheral metabolic flexibility through which SGLT2 inhibition mediates myocardial protection in HFpEF. We have been funded by the Merck **Sharp & Dohme Corp. Research Foundation** via an investigator-initiated study (IIS) to determine if the SGLT2 inhibitor, ertugliflozin, alters cardiac metabolism compared to placebo.

3. STUDY DESIGN

The EMMED-HF trial will be a single blinded (to patient), randomized, parallel group, active controlled, single center experimental design. 52 subjects with HFpEF and DM2 will comorbidities will be recruited to participate (N = 26 ertugliflozin group, N = 26 placebo group) with a 12 week study intervention period.

Enrollment/Randomization procedure

Subjects will be screened by qualified practitioners for eligibility to participate in the EMMED-HF clinical study. Once the subject has been determined to be eligible, an enrollment visit will be scheduled. Those subjects that meet the inclusion criteria and do not possess any exclusion criteria will be deemed eligible for enrollment by key study personnel and then undergo randomization to treatment arm. Randomization into treatment group will occur at baseline at a 1:1 ratio.

Primary endpoint

The primary endpoint is to assess the degree of change in peak exercise oxygen uptake (peak VO2, ml/kg/min) as measured by metabolic gas exchange during a MRIcardiopulmonary exercise test (CPET-ExMR) protocol.

Secondary endpoints

Change in LV mass index (gm/m2) measured by MRI imaging will be a pre-specified secondary endpoint. An additional pre-specified secondary endpoint will be fasting serum β -hydroxybutyrate (ketone body).

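### LV mass endpoint is defined in gm/m2 with no stated divisor but sized in absolute gm; if the divisor uses Visit #3 weight, greater weight loss on ertugliflozin would bias the comparison towards no effect

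*Combined protocol and SAP*

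**What the plan says.** The endpoint appears on two scales.

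- **Indexed.** Section 1 (Aim 1) plans peak VO2 as primary "with change in LV mass (gm/m2) as a pre-specified secondary endpoint". Section 3 (Secondary endpoints) states: "Change in LV mass index (gm/m2) measured by MRI imaging will be a pre-specified secondary endpoint".
- **Absolute.** Section 7.2 says: "A secondary endpoint of left ventricular mass by CMRI (measured concurrently to VO2 during Ex-CMR protocol) will be measured". Its text gives the target as "A reduction of LV mass by 10 gm has been reported as a significant marker of clinical response" and concludes, "For a power of 80% assuming 5% type I error", that "we must enroll 20 subjects to detect a 10 gm change in LV mass assuming a standard deviation of 9.6 gm". The table that follows, whose N column is headed 90% power, has the row "MRI measured LV Mass (gm) 24 5 4 14": reference 24, change 5 gm, SD 4 gm, N 14.

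No section says whether m2 means body surface area or height squared, which formula applies, or which visit's weight enters it. The schedule in section 4.3 records height and weight at screening, baseline and Visit #3. Section 4.4 lists LV mass among the MRI measurements, so grams will be available. Section 2 states that "SGLT2 inhibitors induce a loss of 50-100 grams of glucose through urinary excretion daily", and section 4.4 sets treatment at 84 days. Weight loss on the study drug is not quantified, and no analysis separates it from change in LV mass.

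**The concern.** A per-m2 index is usually read as mass divided by body surface area. If that area is recalculated from the weight at each visit, the divisor is a post-randomisation quantity that treatment may alter. A drug that removes glucose in the urine can be expected to lower weight to some degree. If weight falls more on ertugliflozin than on placebo, the index rises on ertugliflozin for a heart of unchanged mass. Randomisation cannot balance this, because it arises after allocation.

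The error runs against the drug, on the only pre-specified structural endpoint. Separately, an endpoint defined on one scale and sized on another leaves the analyst a choice of scale that could be made after the data are seen.

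**Working it through.** **1. The plan's own figures.** For two means, N per arm = 2 × (z for alpha + z for power)² × (SD/change)², two-sided 5%.

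- Table, 5 gm and SD 4 gm at 90%: 2 × (1.960 + 1.282)² × (4/5)² = 13.5, so 14 per arm. The stated 14 reproduces as a per-arm number (15 with the t distribution).
- Text, 10 gm and SD 9.6 gm at 80%: 2 × (1.960 + 0.842)² × (9.6/10)² = 14.5, so 15 per arm or 30 in total (16 and 32 with the t distribution). The stated 20 does not reproduce at 80%. It does reproduce at 90%, per arm: 2 × (1.960 + 1.282)² × 0.9216 = 19.4, so 20.

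Both calculations are in grams. The two pairs of inputs conflict, so they are kept apart below.

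**2. How much weight could be lost.** The documents give only 50-100 g of glucose a day and 84 days. Assume 4 kcal per g, 7,700 kcal per kg of body weight and no compensatory eating:

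- 50 × 4 × 84 = 16,800 kcal; /7,700 = 2.2 kg
- 100 × 4 × 84 = 33,600 kcal; /7,700 = 4.4 kg

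With no compensation assumed, these are ceilings. A range of 1-4 kg for the between-arm difference is used.

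**3. Effect on the index.** Assume height 170 cm, BMI 33 (inside the eligible range of 25-42), hence 95.4 kg; LV mass 120 gm; stable placebo weight; Mosteller area = √(cm × kg / 3600).

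- Visit #2 area: 2.122 m2
- After 2 kg loss: 2.100 m2; unchanged mass reads 1.07% higher (+0.60 gm/m2)
- After 4 kg loss: 2.077 m2; unchanged mass reads 2.17% higher (+1.22 gm/m2)

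For a true fall of d grams from mass M, the share hidden = ((M − d)/d) × (Visit #2 area / Visit #3 area − 1). With M = 120 the multiplier is 110/10 = 11 for 10 gm and 115/5 = 23 for 5 gm.

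| Extra weight loss on drug | 10 gm (text): fixed → same-visit divisor, gm/m2 | Hidden | 5 gm (table): fixed → same-visit divisor, gm/m2 | Hidden |
|---|---|---|---|---|
| 1 kg | −4.71 → −4.44 | 5.8% | −2.36 → −2.07 | 12.2% |
| 2 kg | −4.71 → −4.16 | 11.7% | −2.36 → −1.78 | 24.5% |
| 4 kg | −4.71 → −3.59 | 23.8% | −2.36 → −1.18 | 49.8% |

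At BMI 33, varying LV mass over 100-150 gm and weight loss over 1-4 kg, the hidden share runs from 5% to 30% of 10 gm and from 10% to 63% of 5 gm.

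**4. Power at 26 per arm.** Two-sided 5% t test, all participants evaluable, SD divided by the Visit #2 area (9.6/2.122 = 4.52; 4/2.122 = 1.89 gm/m2). Noncentrality = (effect/SD) × √(26/2).

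| Divisor | 10 gm, SD 9.6 | 5 gm, SD 4 |
|---|---|---|
| Grams, or fixed divisor | 95.8% | 99.3% |
| Same-visit area, 2 kg | 90.2% | 91.6% |
| Same-visit area, 4 kg | 80.1% | 60.2% |

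**5. Other divisors.** Height squared or Visit #2 area does not change with weight, so the hidden share is zero.

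**The case against.** The strongest reply is that the bias is conditional twice over. It needs the divisor to be body surface area, and it needs that area to be recalculated at Visit #3; the plan says neither. An analysis that followed section 7.2 literally would use grams and hide nothing. The weight loss is also inferred: the glucose figure is for the drug class, and the conversion allows for no extra eating. All of this stands, which is why the firm part of the finding is the mismatch of scales and the undefined divisor, with the bias as an illustration.

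The consequence is also modest. At a 2 kg difference, power stays above 90% for either set of inputs. The bias is towards no effect on a secondary endpoint, so it cannot manufacture a benefit. That stands too.

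A third argument is that the index may be the better question: if the heart shrinks simply because the body does, grams credit the drug with that and a same-visit index partly removes it. This is a fair point about what is being estimated. It does not settle the matter, because the plan itself sizes the endpoint in grams, and it can be met by reporting both.

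A reader might infer that the trial will mask regression, or that a single share of a 5-10 gm target is lost. The documents support neither. They do not commit to a same-visit divisor, and 5 gm and 10 gm are two conflicting planning inputs, not the ends of a planned range.

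**Conclusion.** The point holds in conditional form. What the documents establish is that sections 1 and 3 define the LV mass endpoint in gm/m2, section 7.2 describes and sizes it in gm, and nothing defines the divisor. If body surface area from Visit #3 weight is used, the between-arm difference is biased towards no effect to the extent that weight falls more on ertugliflozin.

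Under the stated assumptions about body size, heart size and placebo weight, the loss ranges from minor (2 kg, measured against 10 gm) to about half the effect (4 kg, measured against 5 gm). The upper end is close to the no-compensation ceiling and should not be taken as expected. This is a cheap improvement to a secondary endpoint, not a threat to the trial's primary result.

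**What to change.** - In sections 1 and 3, name the secondary endpoint as change in absolute LV mass (gm) from Visit #2 to Visit #3, compared between arms with adjustment for Visit #2 LV mass. This matches the scale of section 7.2.
- If an index is preferred, state the formula and divide the mass at both visits by the same quantity: Visit #2 body surface area, or height.
- Report the same-visit gm/m2 index as supportive, alongside weight change by arm.
- In section 7.2, add the baseline-adjusted comparison and settle on one change, SD, power and per-arm N for LV mass, replacing the conflicting 10/9.6 and 5/4 gm inputs.

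The cost is wording only: mass, height and weight are already scheduled, and no visit, scan or participant is added. One small downside is that absolute mass also counts any fall that merely follows loss of body size; the supportive same-visit index would show this.
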